### **5.2.8. Patient-Reported Outcomes**

#### **5.2.8.1. Symptoms of Infection with Coronavirus-19 (SIC)**

The SIC is a disease-specific patient-reported outcome (PRO) instrument that is completed by the participant, self-administered. The SIC has a total of 30 items assessing signs and symptoms of COVID-19. The first 25 items, the participant indicates “yes” or “no” if they have a symptom and if “yes” report a severity from 0 (none) to 10 (worst possible). The second part has the participant

enter their temperature, and the third part has the participant record “yes” or “no” (absence or presence of additional signs and symptoms). The analyses are conducted in two ways, by part 1, part 2 and part 3, scored separately, and also grouped into related categories for composite scoring.

#### SIC Analysis Approach One:

- Part 1 (25 symptoms): Each symptom is present or absent (0), and if present rated on a 10 point scale ranging from 0 (None) to 10 (Worst possible).

The **symptom score** is the mean score of all items on the SIC for each day, during the COVID-19 episode.

The **symptom duration** is the period from the first day of symptoms till the last day with symptoms in Days (calculated as last day with symptoms – first day of symptoms + 1).

The **symptom AUC** is the area under the curve for the complete COVID-19 episode.

The **peak symptom score** is the maximum of all the symptom scores during the COVID-19 episode.

- Part 2: Fever/ temperature.

**Fever** will be scored (fever score) as the maximum recorded temperature for each day during the COVID-19 episode.

**Fever** will be coded as ‘Present’ if the fever score is  $\geq 38.0\text{ }^{\circ}\text{C}$  or  $\geq 100.4\text{ }^{\circ}\text{F}$  and ‘Absent’ otherwise.

The **total fever days** is the number of days with fever present during the COVID-19 episode.

**Fever duration** will be the period from the first day with fever till the last day with fever in Days (calculated as last day with fever – first day of fever + 1).

The **peak fever** is the maximum fever score during the COVID-19 episode.

The **fever AUC** is the AUC of fever score during the total of fever days of the COVID-19 episode. (For the AUC if there is a single missing day between days with fever the missing day will be ignored, ie, interpolation will be used in the calculation of the AUC.)

- Part 3: Each of the 3 specific symptoms is either present (1) or absent (2).

The **specific symptom score** is the mean of all scores during the COVID-19 episode.

The **specific symptom duration** is the duration of specific symptoms during the COVID-19 episode from the first day with a specific symptom until the last day with a specific symptom in Days (calculated as last day with a specific symptom – first day of a specific symptom + 1).

The **total specific reported symptom score** is the mean of all scores during the COVID-19 episode at which a subject has reported at least one specific symptom.

Note 1: For Part 1, total scores will be calculated based on the number of assessments completed by the participant per day and in cases where more than 75% of the items needed to calculate the score is not collected (reported as no answer to the part 1 Yes/No possibility AND no severity rate), then the value for that score will be set to missing. For example, if a participant has responded to 7 or more out of the 25 symptom scale questions the score will be the mean of the available questions. If the participant has only completed 6 or less of the questions then the symptom score will be set to missing, unless a subject has only provided responses ‘Yes’ to all of the answered questions (then it is assumed that the subject only noted the pertinent symptoms for that day). In case of missing severity rate and the answer was ‘yes’ the rate will be imputed by ‘5’.

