### 5.2.8.2. Analysis Methods

SIC scores will be analyzed for participants with any COVID-19 episode, based on the programming algorithm, for each study dose cohort.

For continuous variables, either boxplots or plots of means with standard errors by time point (starts since onset of COVID-19 episode) will be presented per study dose cohort of the risk set. A barchart of the peak SIC score will also be provided per study dose cohort of the risk set.

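### The fever AUC integrates absolute body temperature over fever days with nothing subtracted, so it largely duplicates the count of fever days

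*SAP*

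**What the plan says.** The definitions are in SAP Section 5.2.8.1, SIC Analysis Approach One, Part 2.

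- **Fever score.** Fever "will be scored (fever score) as the maximum recorded temperature for each day during the COVID-19 episode". This is an absolute temperature.
- **Fever day.** A day is coded as fever present when the score reaches 38.0 °C or 100.4 °F. The threshold is used only for this coding and is not a reference line for the AUC.
- **Fever AUC.** It "is the AUC of fever score during the total of fever days of the COVID-19 episode". For a single missing day between fever days, "the missing day will be ignored, ie, interpolation will be used in the calculation of the AUC". The SAP names no integration rule. It also gives no rule for a one-day fever or for fever days separated by days without fever.
- **Neighbouring measures.** Total fever days "is the number of days with fever present during the COVID-19 episode", and peak fever "is the maximum fever score during the COVID-19 episode". Fever duration, from first to last fever day, is defined as well.

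Section 5.2.8.2 states how the scores are shown: "For continuous variables, either boxplots or plots of means with standard errors by time point", per study dose cohort, plus a bar chart of the peak SIC score. There is no testing.

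**The concern.** An AUC is meant to combine height and duration in one measure of burden. That works when zero on the scale means no symptom. The Part 1 symptom score and the severity-rated composites meet this condition, because they run from 0 to 10 and 0 means the symptom is absent. Body temperature in degrees Celsius does not: its zero lies far below any observed value. Integrating it over fever days gives every such day a large fixed weight and leaves little room for the degree of fever.

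This matters within the diary analysis because fever is left out of the Constitutional composite on the ground that Part 2 handles it separately. The AUC is the only Part 2 measure built to combine height with duration. If it mostly repeats the number of fever days, it adds almost nothing to measures already defined beside it, and it can order participants differently from what a reader expects of a burden score.

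**Working it through.** The SAP gives no numerical value for the fever AUC, so there is no figure to reproduce. The check applies the written definition to simple cases.

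**Inputs.** The SAP supplies the daily maximum temperature T, the 38.0 °C threshold and the restriction to fever days. The upper limit of 41.0 °C is an assumption. Since the integration rule is not named, both plausible rules are used. For n consecutive fever days at constant T:

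- trapezoid (suggested by the interpolation sentence): AUC = (n − 1) × T
- daily sum: AUC = n × T

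**1. Height against day count**

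- At fixed n, the largest possible ratio is 41/38 = 1.079, or 7.9%. With a ceiling of 40 °C it is 40/38 = 1.053. Each further degree of ceiling adds 1/38, or 2.6 percentage points.
- From 3 to 4 days at the same T, the trapezoid goes from 2T to 3T (+50%) and the daily sum from 3T to 4T (+33%).

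**2. Ranking**

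| Fever | Trapezoid | Daily sum | Daily sum of (T − 38.0) |
|---|---|---|---|
| 5 days at 38.1 °C | 4 × 38.1 = 152.4 | 5 × 38.1 = 190.5 | 5 × 0.1 = 0.5 |
| 3 days at 40.5 °C | 2 × 40.5 = 81.0 | 3 × 40.5 = 121.5 | 3 × 2.5 = 7.5 |

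The milder fever scores higher under both rules. On excess temperature the order reverses.

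**3. How far one extra day carries.** Compare n days at 41.0 °C with n + 1 days at 38.0 °C.

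- Trapezoid: 38n > 41(n − 1) when 3n < 41, so for n up to 13 (494 against 492 at n = 13).
- Daily sum: 38(n + 1) > 41n when 3n < 38, so for n up to 12 (494 against 492 at n = 12).

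**4. One-day fever.** The trapezoid gives 0 × T = 0, whether T is 38.0 or 40.0 °C. The daily sum gives 38.0 and 40.0.

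**5. Non-adjacent fever days.** Take fever days 1, 2 and 5 at 39.0, 39.5 and 38.5 °C, with no fever on days 3 and 4. A trapezoid drawn across the gap gives 39.25 + 3 × 39.0 = 156.25. The daily sum gives 117.0. The SAP does not say which applies.

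**6. Simulation on assumed inputs.** Fever days were drawn as 1 + Poisson with mean 1.5, 3 or 5, and the daily excess over 38 °C as Gamma (shape 2, scale 0.4) capped at 3 °C.

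- R² of the AUC on the number of fever days was at least 0.9998 (trapezoid) and 0.9997 (daily sum).
- R² of the trapezoid AUC on mean fever temperature was below 0.001.
- For excess over 38 °C summed by day, R² on the number of days was 0.56 to 0.63.

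**The case against.** Several stronger readings are tempting, and the SAP does not support them.

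- **A one-day fever always scores zero.** This follows only under the trapezoid. The interpolation sentence suggests that rule but was written to deal with gaps. What is certain is that the single-day case is unspecified.
- **The AUC cannot tell high fever from low.** It can: at equal duration the higher fever always scores higher, by up to about 8% on the assumed range. Moreover, any cumulative measure trades height against duration. On excess over 38.0 °C, ten days at 38.5 °C score 10 × 0.5 = 5.0, against 3.0 for one day at 41 °C. The fault is the weighting, not the fact that a long low fever can outrank a short high one.
- **Information on fever height is lost.** Peak fever is defined separately, next to total fever days and fever duration.
- **The severity-of-breakthrough objective is compromised.** The estimand table in Section 1.1 summarises that objective by the percentage of severe/critical cases and the percentage of long cases. Section 5.2.7 implements those two ratios, and neither uses the fever AUC. Section 5.2.8.2 specifies no display of the fever AUC in particular, and Sections 5.1 and 5.2 rule out group comparisons.
- **Celsius and Fahrenheit values would be mixed.** Raw Fahrenheit values would inflate the AUC (100.4/38.0 = 2.64 at the threshold), but the SAP gives the two thresholds as equivalents and nothing says unconverted values would be pooled.

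A fair objection to the remedy also stands: with a reference of exactly 38.0 °C, four days at 38.0 °C score 0 although each is coded as fever present.

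None of this answers the main point. Day-count dominance and the ranking in steps 1 to 3 hold under either integration rule.

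**Conclusion.** The point holds as a minor weakness of definition. As written, the fever AUC is close to a rescaled count of fever days: height of fever moves it by at most about 8% at a fixed count, while a fourth fever day moves it by 33% to 50%. The 8% and the 12-to-13-day crossover rest on the assumed ceiling of 41 °C, and the R² values rest on the simulated distributions. The zero for a one-day fever is conditional on the trapezoid. No stated objective or conclusion of the open-label analysis depends on this variable. Correcting it is worthwhile because it would turn a near copy of an existing measure into one that reflects both height and duration.

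**What to change.** Redefine the fever AUC as the sum over episode days of max(0, daily maximum temperature in °C − reference), with the reference stated. Put all temperatures in one unit first, and keep the planned interpolation of a single missing day. Days without fever between fever days then need no special rule.

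The daily sum is part of the fix. Subtracting 38.0 °C but keeping a trapezoid over fever days would still give 0 for a one-day fever.

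The reference is a convention. With 38.0 °C, days at exactly the threshold contribute nothing. A value just below it avoids that: with 37.9 °C, four days at 38.0 °C score 4 × 0.1 = 0.4. In that case the SAP should add that only days coded as fever contribute, so that a reading between the reference and the threshold is not counted.

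The cost is one sentence in Section 5.2.8.1 and one derivation, with no new data. Alternatively, drop the fever AUC and rely on peak fever, total fever days and fever duration.

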### SIC Analysis Approach Two: Composite Scoring

For the purpose of computing the SIC composite scores, the 25 SIC symptom items with severity ratings (part 1) are scored such that item scores range from 0 (“No,” ie, not experienced; or “None”) to 10 (“Worst possible”). Except for the Sensory score, SIC composite scores are computed as the average of the symptom severity ratings for each set of items (Constitutional [where C7 = 0 if NO, 10 if YES], Gastrointestinal, Musculoskeletal, Neurological, Respiratory, Upper Respiratory, Lower Respiratory). The average composite score is a number between 0 and 10 (inclusive). Because all SIC composite scores are in the same metric as the item-level severity ratings, this links the interpretation of the SIC composite scores to the items, with higher scores reflecting worse symptoms.

**Constitutional.** The SIC includes 7 Constitutional items, 2 of those items use a dichotomous response scale (C6: Fever, C7: Uncontrollable body shaking/shivering). The constitutional score includes C7 as well as the 5 Constitutional items that use the 11-point severity rating scale (C1: Feeling generally unwell, C2: Fatigue (tiredness), C3: Chills, C4: Skin rash, C5: Eye irritation/discharge). To allow scoring in the 0-10 item metric, a “Yes” to C7 was re-coded to a value of 10 given the severe nature of rigors. The SIC Constitutional score is the equally weighted average of 6 Constitutional items (excluding C6). Fever as described above is analyzed on its own (part 2 of SIC Analysis Approach1):

*Constitutional* = average of (C1, C2, C3, C4, C5, C7) where C7 = 0 if NO, 10 if YES

**Gastrointestinal.** The SIC Gastrointestinal score is an equally weighted average of the severity ratings of all 5 SIC items related to Gastrointestinal symptoms (G1: Diarrhea, G2: Vomiting, G3: Nausea, G4: Abdominal/stomach pain, G5: Loss of appetite):

*Gastrointestinal* = average of (G1, G2, G3, G4, G5)

**Musculoskeletal.** The SIC Musculoskeletal score is an equally weighted average severity ratings of 3 items (M1: Physical weakness, M2: Muscle aches/pains, M3: Joint aches/pains):

*Musculoskeletal* = average of (M1, M2, M3)

**Neurological.** The SIC Neurological score is an equally weighted average severity ratings of 3 items (N1: Headache, N2: Feeling faint, N3: Problems thinking clearly/brain fog):

*Neurological* = average of (N1, N2, N3)

**Sensory.** Two SIC items (N4: Decreased sense of smell, N5: Decreased sense of taste) are a 2-item Sensory composite score with 3 possible values:

*Sensory* = 0 if NO to both N4: Decreased sense of smell and N5: Decreased sense of taste

= 5 if YES to only one of the 2 items (and NO to the other item)

= 10 if YES to both items

**Respiratory.** The SIC Respiratory score is an equally weighted average severity rating of all 9 Respiratory items (R1: Cough, R2: Shortness of breath, R3: Sore throat, R4: Nasal congestion, R5: Wheezing, R6: Runny nose, R7: Sneezing, R8: Chest congestion, R9: Chest pain/pressure/tightness):

*Respiratory* = average of (R1, R2, R3, R4, R5, R6, R7, R8, R9)

In addition, separate Lower Respiratory and Upper Respiratory SIC scores were computed:

*Lower Respiratory* = average of (R1, R2, R5, R8, R9)

*Upper Respiratory* = average of (R3, R4, R6, R7)

For each composite the following analysis will be conducted:

The **<Composite name> symptom score** is the mean of all scores for each day, during the COVID-19 episode.

The **<Composite name> symptom duration** is the period from the first day of symptoms till the last day with symptoms in Days (calculated as last day with symptoms – first day of symptoms + 1).

The **<Composite name> symptom AUC** is area under the curve for the complete COVID-19 episode.

The **<Composite name> peak symptom score** is the maximum of all the symptom scores during the COVID-19 episode.

After completing the SIC, each day the participant completed a Patient Global Assessment of Severity, asking them to rate the severity of their symptoms in the last 24 hours with responses of “No Symptoms”, “Mild”, “Moderate” or “Severe”

### 5.2.8.2. Analysis Methods

SIC scores will be analyzed for participants with any COVID-19 episode, based on the programming algorithm, for each study dose cohort.

For continuous variables, either boxplots or plots of means with standard errors by time point (starts since onset of COVID-19 episode) will be presented per study dose cohort of the risk set. A barchart of the peak SIC score will also be provided per study dose cohort of the risk set.

### 5.3. Efficacy Analysis of the Open-Label Passive Follow-up Phase

Since PA7, suspected COVID-19 cases are followed up in a passive manner. There are no nasal swabs and no signs and symptoms collected for suspected COVID-19. Suspected COVID-19 cases are collected via a passive safety reporting of adverse events.

The efficacy analysis of the open-label passive follow-up phase includes all COVID-19 data collected as adverse events from the date that the site approves PA7 until study end date. The endpoints of interest are: symptomatic COVID-19, severe COVID-19, COVID-19 requiring medical intervention, and COVID-19 related death.

Under PA7, the definition of symptomatic COVID-19 is adverse events with a preferred term that is included in the narrow scope of the SMQ of “COVID-19”. Severe COVID-19, is defined by serious adverse events with a preferred term that is included in the narrow scope of the SMQ of “COVID-19”. COVID-19 requiring medical intervention is defined by hospitalized adverse events with a preferred term that is included in the narrow scope of the SMQ of “COVID-19”. COVID-19 related death is defined by the WHO assessment from the Global Medical Safety group.

The population used for the analysis in the open-label passive follow-up phase is the full analysis set who are still active in the study at the time the site approves PA7 (FAS7). Same study dose cohorts as the open-label active follow-up phase are presented (Section 5.2.1).

Similarly as for the open-label active follow-up analysis, a demographic table will be provided for the FAS7 population.

For each of the COVID-19 cases as defined above, the number of cases and incidence per 100 person-years will be presented for each study dose cohort. The denominator for the incidence rates is the number of person years in the considered period for a certain regimen (incidence per 100 person years/period). The follow-up time included for the participants will end at the period end date (study end or discontinuation date). Note that participants can have multiple COVID-19 events within the same period.

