### **1.1. Objectives, Endpoints**

The list of objectives and endpoints for the open-label active surveillance phase and for the open-label passive follow-up phase can be found in PA7. Note that no efficacy evaluations or group comparisons will be performed. All objectives will be evaluated using descriptive statistics.

As of protocol amendment 2, subjects were allowed to receive vaccination outside of the study while still following the same protocol scheduled procedures as those subjects that remained in the study with the Ad26.COV2.S vaccine. The safety for subjects that received other vaccines outside of the study will also be described. No tabulations of efficacy data following vaccines received outside of the study will be provided.

The exploratory endpoints associated with the correlate of risk/efficacy objective will not be evaluated in this study. Correlate of risk/efficacy objectives will be evaluated in the context of study COV3001.

The exploratory endpoints associated with immunogenicity objectives will not be evaluated in the open-label active surveillance phase.

Estimands for the open-label active surveillance analysis:

Objectives	Endpoints/Variable	Population	Intervention	Intercurrent events	Summary measure
Safety	SAEs, AEIs and AESIs from study start until PA7 site approval	Adults>= 18 years old	Ad26.COV2.S, placebo, one or more doses of mRNA + Ad26.COV2.S OR one or more doses of non-mRNA + Ad26.COV2.S, mixed schedule	LTFU	Number of subjects with events and incidence rates per 100 person years per reporting period
Molecularly confirmed a , symptomatic COVID-19 b	Symptomatic COVID-19 according to mild, moderate or severe programmed algorithmic definition, with onset at least 28 days after last vaccination.	Adults>= 18 years old	Single dose Ad26.COV2.S  Two doses Ad26.COV2.S (maximum of 70 days between doses)  Booster dose Ad26.COV2.S (minimum of 71 days between doses)	LTFU-Outside vaccinations	Number of subjects with events and incidence rates per 100 person-years

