[figure not shown]
Objectives	Endpoints/Variable	Population	Intervention	Intercurrent events	Summary measure
Safety	SAEs, AEIs and AESIs from PA7 site approval until end of the study	Adults>= 18 years old	Ad26.COV2.S, placebo, one or more doses of mRNA + Ad26.COV2.S OR one or more doses of non-mRNA + Ad26.COV2.S, mixed schedule	LTFU	Number of subjects with events and incidence rates per 100 person years per reporting period
COVID-19 in terms of (S)AEs, MAAEs, hospitalizations and fatal AEs linked to COVID-19	
 
SAEs and AEs linked to COVID-19
 
MAAEs linked to COVID-19
 
SAEs linked to COVID-19 that require hospitalization
 
Fatal AEs linked to COVID-19
 
	Adults>= 18 years old	Single dose Ad26.COV2.S Two doses Ad26.COV2.S (maximum of 70 days between doses) Booster dose Ad26.COV2.S (minimum of 71 days between doses)	LTFU-Outside vaccinations	Number of subjects with events and incidence rates per 100 person-years
Immunogenicity of Ad26.COV2.S at available timepoints	
 
Analysis of antibodies binding to the SARS-CoV-2 S protein by ELISA
 
Analysis of SARS-CoV-2 neutralizing antibody titers as measured by psVNA and/or wtVNA
 
	Adults>= 18 years old	Two doses Ad26.COV2.S	LTFU- Outside vaccinations	GMR, responder rate  GMR, responder rate
Correlate of immunity	
 
Analysis of binding antibody titer measured by S-ELISA and/or MSD assay, as available for participants having COVID-19 compared to non-infected participants
 
Analysis of SARS-CoV-2 neutralizing antibody titers measured by psVNA or wtVNA,
 
	Adults>= 18 years old	Two doses Ad26.COV2.S	LTFU- Outside vaccinations	Not evaluated in this study.

Objectives	Endpoints/Variable	Population	Intervention	Intercurrent events	Summary measure
	as available for participants having COVID-19 compared to non-infected participants				

LTFU: Lost to follow-up

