- Booster dose schedule cohort: participants who, during the course of the study, have received only a single dose of the Ad26.COV2.S vaccine and received a booster vaccination under PA6, preferably within 6 to 12 months after the initial vaccination, with a minimum of 3 months after the initial vaccination with Ad26.COV2.S. The number of days between first Ad26.COV2.S vaccination and second Ad26.COV2.S vaccination must be a minimum of 71 days to qualify for the booster dose cohort.

With PA7, requirements for COVID-19 episode reporting are changed, ie, a passive surveillance approach is adopted, defined as following up on new COVID-19 episodes during scheduled phone calls with the participants. Participants will enter this phase on the date of site approval of PA7. The data collected in the passive follow-up phase will be analyzed separately from the open-label active follow-up phase and the efficacy analysis will be described in a separate section within this SAP. For efficacy the same study cohorts as in the open-label active phase are used. Efficacy following a COVID-19 vaccination given outside of the study will not be assessed. The safety data after PA7 approval will also be presented separately from the safety data under the active follow-up. The same vaccination groups are used as for the open-label active follow-up phase.

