#### **5.2.5. Follow-up for Efficacy Endpoints**

Median, minimum, maximum, and interquartile range of the follow-up time in the observational period will be provided by study dose cohort of the efficacy risk set. The reason for the end of follow-up will also be included in the table.

For subjects in the one-dose schedule cohort the follow-up time is calculated from date of unblinding. If the date of the first dose is after the date of unblinding, then the follow-up time will start at the date of first dose. For subjects in the two-dose schedule cohort and subjects in the booster dose schedule cohort the follow-up time starts from the date of the second dose. If the date of the second dose is prior to unblinding then the follow-up time will start from the date of unblinding. The first 28 days after vaccination are excluded. Additionally follow-up time from first study vaccination and follow-up time from last Ad26.COV2.S vaccination will also be presented by study dose cohort of the efficacy risk set.

The follow-up time for an individual will be censored at i) the date of receipt of another authorized/approved COVID-19 vaccine, including the Janssen COVID-19 vaccine if received outside of the study, ii) the date of study discontinuation or completion, iii) 30 days prior to the date of study site approval for PA7, or iv) the date the endpoint was observed, whichever occurred first. Additionally, for subjects in the single-dose schedule cohort the date of a second

Ad26.COV2.S vaccination will be considered as a reason for censoring and for subjects in the two-dose and the booster dose cohorts, the date of a third Ad26.COV2.S vaccination will be considered as a reason for censoring.

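### Section 5.3 ends passive-phase follow-up only at study end or discontinuation, which contradicts the SAP's own exclusion of efficacy data after an outside COVID-19 vaccination

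*SAP*

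**What the plan says.** Section 5.3 sets four things for the passive phase.

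- Population: FAS7, defined in Table 4 as FAS members still active when their site approves PA7. Outside vaccination is not an exclusion.
- Cases: "The efficacy analysis of the open-label passive follow-up phase includes all COVID-19 data collected as adverse events from the date that the site approves PA7", up to study end. It adds: "Note that participants can have multiple COVID-19 events within the same period".
- Denominator: "The denominator for the incidence rates is the number of person years in the considered period for a certain regimen".
- End of follow-up: "The follow-up time included for the participants will end at the period end date (study end or discontinuation date").

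The cohorts are those of Section 5.2.1. There, a one-dose participant leaves the cohort at the second Ad26.COV2.S dose. Section 5.2.1 names no exit at an outside vaccination.

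Other parts of the SAP speak to the same analysis. Section 1.1 states: "No tabulations of efficacy data following vaccines received outside of the study will be provided". The passive-phase paragraph of Section 1.2 states: "Efficacy following a COVID-19 vaccination given outside of the study will not be assessed". Section 1.2 also ends one-dose membership at an outside vaccination. The passive estimand for COVID-19 lists "LTFU-Outside vaccinations" as intercurrent events, gives no strategy for them, and summarises by the number of subjects with events.

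For the active phase, Table 5 and Section 5.2.5 stop follow-up at an outside vaccination and at the second Ad26.COV2.S dose in the one-dose cohort. For the two-dose and booster cohorts, "the date of a third Ad26.COV2.S vaccination will be considered as a reason for censoring".

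**The concern.** The only operational stopping rule for the passive efficacy rates omits the event that the rest of the SAP says must end them. A programmer who follows Section 5.3 keeps counting after an outside vaccination. One who follows Sections 1.1 and 1.2 stops. They would report different numerators and denominators under the same cohort labels.

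These counts and rates are the efficacy output of the passive phase, which the Introduction identifies as the end-of-study analysis. A rate labelled as one-dose, two-dose or booster Ad26.COV2.S would then partly describe people protected by another vaccine.

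**Working it through.** The SAP states no figure on this point: the open-label phase has no sample size and no hypothesis. The check is therefore a comparison of rules, followed by an illustration on assumed values.

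**Rules side by side**

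| Event | Active phase (Table 5, 5.2.5) | Section 5.3 | Elsewhere in the SAP |
|---|---|---|---|
| Outside vaccination before the period starts | Excluded | Not mentioned; FAS7 does not exclude it | 1.1 and 1.2: not tabulated, not assessed |
| Outside vaccination during the period | Censored | Not a stop | As above; 1.2 also ends one-dose membership; an intercurrent event in the estimand |
| Second Ad26.COV2.S dose, one-dose cohort | Censored | Ends membership, through 5.2.1 | 1.2 ends membership at the booster |
| Third Ad26.COV2.S dose, two-dose and booster cohorts | Censored | Not mentioned | 1.2: participants with two doses are not eligible for the study booster |
| First COVID-19 event | Ends follow-up | Does not; multiple events allowed | Estimand counts subjects |
| Discontinuation or study end | Stops | Stops | Consistent |

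The first two rows are contradictions, the fourth is a gap, and the fifth is a mismatch with the estimand.

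**One participant.** Take a 1-year passive phase, an outside vaccination at 0.25 years and a COVID-19 adverse event at 0.75 years. Section 5.3 read literally gives 1 case in 1.00 person-year. Stopping at the outside vaccination gives 0 cases in 0.25 person-year. A participant vaccinated outside before PA7 approval would add all of their passive time under the literal rule and none under the other.

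**Rate for a cohort.** Let s be the share of cohort person-time after an outside vaccination, and RR the case rate in that time divided by the rate before it. Then

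reported rate / own-regimen rate = (1 − s) + s × RR.

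The SAP gives neither s nor RR, so both are assumptions:

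| s | RR 0.4 | RR 0.7 | RR 1.0 | RR 1.3 |
|---|---|---|---|---|
| 5% | 0.97 | 0.985 | 1.00 | 1.015 |
| 10% | 0.94 | 0.97 | 1.00 | 1.03 |
| 25% | 0.85 | 0.925 | 1.00 | 1.075 |
| 50% | 0.70 | 0.85 | 1.00 | 1.15 |

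**Worked example.** Assume 1000 participants followed for 1 year, 30% vaccinated outside at uniformly spread times, and 10 cases per 100 person-years beforehand. Then s = 0.30 × 0.5 = 0.15, so 850 person-years fall before an outside vaccination and 150 after.

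- RR 0.4: 850 × 0.10 + 150 × 0.04 = 85 + 6 = 91 cases in 1000 person-years, or 9.10 per 100.
- RR 0.7: 85 + 150 × 0.07 = 95.5 cases, or 9.55 per 100.
- Stopping at the outside vaccination: 85 cases in 850 person-years, or 10.0 per 100.

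At RR 1.0 the rate is unchanged, but the case count (100 against 85) and the person-years (1000 against 850) still differ.

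**The case against.** The strongest reply is that the SAP already shows what it intends. Sections 1.1 and 1.2 exclude these data. Section 5.4.3 censors data after Ad26.COV2.S at an outside vaccination, ends each Table 6 period just before the next vaccination, and runs passive follow-up to the end of the phase or of the study. Passive efficacy rests on adverse-event data, and the denominator in Section 5.3 is tied to a regimen. Section 5.2.1 also admits only risk-set members to the cohorts, and the risk sets exclude earlier outside vaccinees.

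Part of this stands. A reader might infer that the plan has settled on crediting outside-vaccine data to the Ad26.COV2.S cohorts. The documents do not support that: they contradict each other.

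The reply does not remove the contradiction. The rules in Section 5.4.3 belong to the safety analysis, and Section 5.3 gives its own meaning of period end in parentheses. The mention of a regimen carries no stopping rule. Section 4 ties the risk sets to the active phase and names FAS7 for the passive phase. Those sets also exclude only vaccination before active observation began, so someone vaccinated outside during it was censored there but is not barred from FAS7.

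Three further readings go too far:

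- That a further Ad26.COV2.S dose is ignored throughout. The one-dose cohort does end at the second dose, through Section 5.2.1. A third dose is unaddressed in Section 5.3 but should be rare, given booster ineligibility after two doses.
- That one illness coded to two preferred terms will be counted twice. This is inferred from an event-merging rule in Section 5.4.6.3 that Section 5.3 does not invoke.
- That the distortion varies by cohort and country by a known amount. The SAP has no data on this, and Section 5.3 plans no results by country.

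**Conclusion.** The point holds as an internal contradiction with a wrong operational rule. The follow-up sentence in Section 5.3 conflicts with Sections 1.1 and 1.2 and with the passive estimand. Followed as written, it yields rates that do not belong to the named schedules.

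The size is unknown. It depends on how much person-time follows an outside vaccination and on the case rate in that time. Over the assumed grid the reported rate runs from 0.70 to 1.15 times the own-regimen rate.

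Because the phase is descriptive, with no hypothesis and no group comparison, the harm is mislabelled rates, case counts and person-years. A reader might infer a biased efficacy estimate or an invalid test, but the SAP plans neither. It is still worth settling before the end-of-study tables are programmed.

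**What to change.** Amend Section 5.3 as follows.

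1. Exclude from the passive dose cohorts any participant with an outside COVID-19 vaccination on or before PA7 site approval.
2. End both person-time and case counting at the earliest of outside vaccination, next Ad26.COV2.S vaccination (second for the one-dose cohort, third for the two-dose and booster cohorts), discontinuation or study end, in line with Table 5 and Section 5.2.5.
3. Match the numerator to the estimand by reporting participants with a first event, with person-time for that rate ending at the event as in the active phase. Show any recurrent episodes separately.

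The cost is a few sentences of SAP text and reuse of the active-phase stopping rules. The downside is fewer person-years: in the example above, 850 instead of 1000 from the outside-vaccination stop alone, and fewer still once earlier outside vaccinees are removed.
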